### A3a. Financial Conflict of Interest

Does any member of study personnel (Investigator (including investigator's spouse and/or dependent children)) that are involved in the design, conduct, or reporting of the research have a Significant Financial Interest (SFI) that would reasonably appear to be affected by the research for which funding is sought and/or associated with an entity/business that would reasonably appear to be affected by the research?

No

### A5. Funding Source:

Organization: VA CENTRAL OFFICE, RR&D

### A6a. Institution(s) where work will be performed:

Michael E. DeBakey Veterans Affairs Medical Center

### A6b. Research conducted outside of the United States:

Country:  
Facility/Institution:  
Contact/Investigator:  
Phone Number:

If documentation of assurances has not been sent to the Office of Research, please explain:

#### **A7. Research Category:**

#### **A8. Therapeutic Intent**

Does this trial have therapeutic intent?

Yes

#### **A9. ClinicalTrials.gov Registration**

Does this protocol/trial require registration on ClinicalTrials.gov due to it: meeting the definition of an Applicable Clinical Trial, being required under the terms and conditions of an award, or being proposed to be published in ICMJE journals?

Yes

Who will be responsible for registering and maintaining the registration of this Applicable Clinical Trial?

The BCM PI will register the trial because either:

- the trial is BCM PI-initiated,
- BCM is the lead site of this multicenter trial, or,
- the industry sponsor has instructed the BCM PI to register the trial, or,
- registration of this trial is required as a term and condition of the reward by the funding agency.

ClinicalTrials.gov Identifier:

NCT05340478

### **Section B: Exempt Request**

#### **B. Exempt From IRB Review**

Not Applicable

### **Section C: Background Information**

Anxiety disorders and posttraumatic stress disorder (PTSD) are highly prevalent among Veterans; estimates indicate that 30-40% of military service members experience at least one anxiety-based disorder, with PTSD being the most prominent. Prevalence estimates for posttraumatic stress disorder (PTSD) in Veterans range from 21-29%. Panic disorder (PD), generalized anxiety disorder (GAD), and social anxiety disorder (SAD) are common in Veterans, with prevalence estimates 6%, 8%, and 15%, respectively. Comorbidity among the anxiety disorders is also high and poses unique challenges to treatment. The process of recovery and community reintegration across the lifespan for Veterans with anxiety-based disorders is a significant problem. Resuming and participating in major social life roles within the community is challenging due to the debilitating nature of anxiety, which often results in avoidance of everyday activities and social withdrawal. Consequently, PTSD and anxiety are associated with substantial impairment in social, vocational, emotional, and physical functioning and high rates of suicide.

Cognitive behavioral therapy (CBT) is the front-line treatment for PTSD and anxiety disorders. Through the combination of psychoeducation, cognitive restructuring, and behavioral exposure to feared stimuli, patients are taught skills to overcome their fears. Although CBT for anxiety is effective, a significant proportion of patients (approximately 50%) do not achieve remission after completing treatment. For example, outcomes obtained from

military and Veteran populations indicate that up to 75% retained a PTSD diagnosis following CBT. Although different explanations exist for poor treatment response, treatment engagement is a common problem for those undergoing exposure-based treatments. LeBeau and colleagues reported that the degree to which adults engaged in CBT exposure exercises outside of session predicted treatment outcomes. Unfortunately, the very nature of anxiety motivates people to engage in avoidance behaviors related to their fears, which can undermine the effectiveness of treatment.

Recent research shows that interpersonal factors between a patient with anxiety and a family member may also function to maintain anxiety symptoms through a process known as accommodation. This occurs when family members adjust their own behaviors to help reduce the distress experienced by their loved one. This may take the form of the family member providing constant reassurance to the patient, using distraction, serving as a safety object by accompanying the patient outside of their comfort zones, warning others how to behave around the patient, and assuming more responsibilities typically handled by the patient. Although well-intentioned, accommodation behaviors by family members are detrimental and directly undermine the effectiveness of CBT approaches by facilitating further avoidance for the patient. Accommodation behaviors are associated with increased symptom severity and functional impairment. Over time, this pattern of responding becomes strenuous and exhausting to the family member and can deteriorate the relationship with the loved one. Thus, when a member of the family has mental illness, it impacts the family as a system by disrupting the equilibrium within that unit. In these instances, family members adjust patterns of how they respond and interact with the individual to restore balance to the family unit.

Despite this knowledge, the primary focus of most current evidence-based CBT approaches for anxiety continue to focus exclusively on treating the symptomatic individual. Only recently have researchers begun investigating brief interventions to target decreasing accommodation behaviors in family members of adult patients. Such interventions provide psychoeducation on how anxiety is maintained and teach family members new skills that will facilitate the patient's recovery from anxiety. These studies, along with results obtained from pediatric samples show that addressing accommodation behaviors in treatment is associated with reduced symptom severity, increased treatment response, satisfaction, and engagement by family, and improved remission rates.

Anxiety disorders and PTSD are highly prevalent among Veterans and service members but there has been limited focus on the development of CBT interventions that incorporate family members in the treatment provided to Veterans. Except for Cognitive-Behavioral Conjoint Therapy for PTSD, which provides treatment to couples in which one or both persons have PTSD, the majority of VA evidence-based psychotherapy (EBP) rollouts focus on treating the individual. Thus, novel and innovative approaches that involve family members and caregivers in treatments provided to Veterans are needed.

## Section D: Purpose and Objectives

This study will examine the feasibility/acceptability of, and satisfaction with, a new intervention for family members of Veterans undergoing CBT for anxiety-based disorders. Adjunctive Family-CBT (AF-CBT) is framed within a family-systems approach, which addresses recovery of the Veteran within the context of the family unit rather than the patient as an individual. AF-CBT provides family members psychoeducation on anxiety and teaches skills that can be used to facilitate the recovery of Veterans who are in the process of completing treatment for anxiety.

A total of 47 Veterans and family member dyads (V/F dyad) will be recruited for this study. Phase 1 will recruit 12 V/F dyads for family members to receive AF-CBT while the Veteran undergoes CBT for anxiety. Each V/F dyad will participate in a post-treatment assessment that includes a semi-structured qualitative interview to gain a deeper understanding of their experience with the intervention and feedback on ways to refine the intervention. In this phase, AF-CBT will be delivered in three separate cohorts (approximately 4 V/F dyad in each cohort). The intervention will be refined using two adaptation frameworks (IM and FRAME) to guide the process, following completion of each cohort. Phase 2 of this study will recruit 35 additional V/F dyads to participate in the finalized version of AF-CBT.

Treatment feasibility, acceptability, and satisfaction will be evaluated via self-report assessment and qualitative interviews. The Family Accommodation Scale for Anxiety (FAS-A) will also be adapted for use with Veterans and administered at baseline and 1-month follow-up. The goal of this study is to further adapt and refine an adjunctive intervention for family members of Veterans who undergo CBT for anxiety. The long-term goal is to examine the effectiveness of AF-CBT as a therapeutic strategy to enhance the effectiveness of exposure-based treatments for anxiety for Veterans.

## **Section E: Protocol Risks/Subjects**

### **E1. Risk Category**

Category 1: Research not involving greater than minimum risk.

### **E2. Subjects**

Gender:

Both

Age:

Adult (18-64 yrs), Geriatric (65+ yrs)

Ethnicity:

All Ethnicities

Primary Language:

English

Groups to be recruited will include:

Patients

Which if any of the following vulnerable populations will be recruited as subjects?

Mentally ill

Vulnerable populations require special protections. How will you obtain informed consent, protect subject confidentiality, and prevent undue coercion?

Project staff will review information about the study with the patient, including the study procedure, patient's rights, risks and benefits of participation, and the methods that will be taken to protect the patient's confidentiality. The patient will have the opportunity to ask questions throughout the process. Patients will be asked to reiterate their understanding of the purpose and procedures related to the study. Study staff will clarify any necessary points and answer questions. Participants will not require a Legally Authorized Representative for this study.

### **E3. Pregnant woman/fetus**

Will pregnant women and/or fetuses (as described in 45 CFR 46 Subpart B) be enrolled in the research?

No

### **E4. Neonates**

Will neonates of uncertain viability or nonviable neonates (as described in 45 CFR 46 Subpart B) be enrolled in the research?

No

### **E5. Children**

Will children be enrolled in the research?

No

## **Section F: Design/Procedure**

### **F1. Design**

Select one category that most adequately describes your research:

c) Pilot

Discuss the research design including but not limited to such issues as: probability of group assignment, potential for subject to be randomized to placebo group, use of control subjects, etc.

This study examines the feasibility and acceptability of, and satisfaction with, a new intervention for family members of Veterans undergoing CBT for anxiety disorders/PTSD. A total of 47 V/F dyads will be recruited. Phase I will focus on refining the AF-CBT intervention, and Phase II will deliver the finalized AF-CBT protocol to V/F dyads.

In phase 1, 12 V/F dyads will be recruited to refine the adapted AF-CBT intervention. Family members will receive AF-CBT while the Veteran undergoes iCBT for anxiety. The AF-CBT intervention will be delivered in

separate cohorts (approximately 4 V/F dyads in each cohort). During the 1-month assessment, information obtained from qualitative interviews with each cohort will subsequently be used to refine the intervention in an iterative process. In phase 2, 35 V/F dyads will be recruited and administered the finalized version of AF-CBT following the same treatment and assessment format. Qualitative interviews will focus on each V/F dyad's experience with the AF-CBT intervention and whether specific components of the intervention facilitated the Veteran's recovery process.

**Inclusion Criteria:**

(1) Veteran at least 18 years old; (2) current diagnosis of at least one anxiety-based disorder: PTSD, PD, SAD, GAD, or Other Specified Anxiety Disorder (based on ADIS-5); (3) moderate-to-poor life enjoyment and satisfaction as indicated by a score of 47 or lower on the Q-LES-Q-SF (4) BAI score of 16 (moderate anxiety) or higher; (5) stable on psychotropic medication for 4 weeks before study participation; and (6) has a family member willing to participate in the study. The identified family member must be an adult over the age of 18 years who either lives with the Veteran or has frequent contact (>3 days/week) and can commit the time to attend the AF-CBT intervention.

**Exclusion Criteria:**

(1) Active symptoms of mania or psychosis at baseline (based on ADIS-5); (2) depression with active suicidal ideation/intent that would preclude treatment (based on ADIS-5 & BDI-II); (3) moderate-to-severe cognitive impairment as indicated by a score below 20 on the SLUMS; and (4) active drug/alcohol abuse during the initial 3-months of study enrollment (otherwise Veterans with comorbid substance/alcohol dependence are study eligible)

## **F2. Procedure**

**Recruitment:** Veterans will be recruited through the Center for Innovative Treatment of Anxiety & Stress (CITRAS) at the Michael E. DeBakey VA Medical Center. CITRAS is an anxiety specialty clinic and receives direct referrals from clinics throughout the main hospital (e.g., General Mental Health Clinic, Post-Deployment Center, Primary Care Mental Health, PTSD Outpatient Clinic) and 11 community-based outpatient clinics (CBOCs). Flyers advertising the study will be posted throughout MEDVAMC and CBOCs, and the study will be advertised through electronic messaging boards throughout the hospital, posters, and VA approved social media outlets.

**Procedure:** Veterans expressing interest in the study will speak with a member of the study team who will provide information about the study. Veterans expressing interest in the study will be pre-screened with the Q-LES-Q-SF and BAI to determine if a moderate level of impairment in general functioning and anxiety are present (this data will not be included in research data set). If so, an appointment will be scheduled for interested Veterans and identified family members to complete a brief joint assessment, which will take about 2 hours. The Veteran will be scheduled for a separate appointment to complete a full baseline evaluation (where the Q-LES-Q-SF and BAI will be re-administered) approximately 2 weeks before receiving treatment. This appointment will last about 2.5 hours. The family member will start AF-CBT within 1-2 weeks of when the Veteran participates in anxiety treatment (delivered over 1 weekend). Approximately 2 weeks after the family member completes AF-CBT, the V/F dyad will meet with a study clinician for a conjoint (1.5 hour) booster session. The V/F dyad will be asked to complete a 1-month follow-up assessment, which will include a qualitative interview regarding their experience with the treatment (approximately 2.5 hours). It is anticipated that most participants will complete the study in approximately 4 months.

**Assessments:** Veterans will undergo two assessments (baseline & 1-month follow-up). The baseline evaluation will include a structured diagnostic interview (ADIS-5) and psychological screening measures to determine general emotional functioning and the presence of specific psychiatric disorders. All assessments will be supervised by a licensed psychologist. Veterans will be informed that study staff will need to access their medical records periodically to track relevant psychiatric and medical information. Protected health information that will be collected from Veterans in this study include: name, address, telephone numbers, dates of appointments related to the study, last four digits of social security number, and voice recordings. Demographic information, medications prescribed, and dates of mental health treatment appointments will also be collected. VA Quality Assurance and BCM IRB personnel responsible for providing general oversight of this study may also have access to research data. Study data regarding individual information that is not in the patient's medical record will remain confidential and inaccessible to other agencies. Family members will also be asked to complete a few brief measures at baseline and 1-month follow-up time points.

**Qualitative Interviews:** All V/F dyads who complete AF-CBT will be invited to participate in a qualitative interview following completion of AF-CBT. The purpose of the interview is to obtain V/F dyads' feedback about AF-CBT.

Collection and analysis of qualitative data will be overseen by Co-I, [name], and interviews will be conducted using a semi-structured interview guide (attachment in Section S) by [name] (consultant). All interviews will be digitally audio-recorded using a microphone linked directly to a VA networked computer. De-identified audio recordings of the interviews will be saved to the MEDVAMC Research folder on the S Drive: Research-Data/[name] Lab. Lighthouse for the Blind will transcribe the audio recordings by accessing the research folder on the S Drive through their contractor PIV card or through receiving files via encrypted e-mail. Transcriptions will be saved to the research folder.

Measures: (1) Community Reintegration of Injured Service Members (CRIS), a commonly used measure of community reintegration following deployment; (2) Beck Anxiety Inventory (BAI) assesses the severity of anxiety symptoms, minimizing those that overlap with depression; (3) DASS; (4) Quality of Life Enjoyment and Satisfaction Questionnaire- Short Form (Q-LES-Q-SF) is a brief, 16-item measure of subjective functioning and satisfaction across a range of life domains including work, leisure activities, social relationships, and physical health; (5) Saint Louis University Mental Status Exam (SLUMS) is an 11-item clinician-administered screening measure of cognitive impairment; (6) Anxiety Disorders Interview Schedule DSM-5 (ADIS-5) is a gold-standard semi-structured clinician interview used to assess for the presence of all anxiety disorders including PTSD. Modules examining the presence of psychosis, mood and substance abuse disorders are also included; (7) Demographic and Military Survey is a brief questionnaire we have used in previous studies that inquires about general demographic and military information. Veterans are asked about their periods of service, deployment dates, whether they seek healthcare outside of VA, and other information pertaining to their education and employment history; (8) Client Satisfaction Questionnaire-8 (CSQ-8) is an 8-item measure that assesses overall treatment satisfaction; (9) Family Accommodation Scale is a 16-item self-report measure of anxiety symptom accommodation during the past month; (10) Couples Satisfaction Index (CSI) assesses satisfaction in the relationship; (11) Revised Dyadic Adjustment Scale (RDAS) assesses several domains of relationship quality; (12) Modified Treatment Evaluation Inventory (MTEI) is a brief 9-item measure that uses a 5-point Likert scale to assess acceptability of treatment components; and (13) Inventory of Psychosocial Functioning (IPS) a measure that assesses functioning across different domains of life. The ADIS-5, SLUMS, Demographics Form will be given at baseline only and the CSQ and MTEI will given at 1-month follow-up only. The remaining measures will be administered at both time points.

Treatments: Veterans will receive iTCBT, which is a transdiagnostic cognitive-behavioral group treatment for anxiety disorders. iTCBT is delivered over two consecutive days (1 weekend), lasting 8 hours each day. A maximum of 6 Veterans may be enrolled per group cycle. iTCBT includes psychoeducation about the nature of anxiety and skills training for changing maladaptive thoughts and behaviors. Family members of Veterans will receive AF-CBT, which is adapted from existing protocols that have been used with non-Veteran adult patients. AF-CBT is a brief intervention and consists of two 2-hour long sessions delivered in small groups of family members (maximum of 6). Two weeks after completion of AF-CBT, a conjoint booster session will be provided to V/F dyads to check in on progress and provide guidance in tailoring intervention components to the V/F dyad. In addition to psychoeducation on anxiety, how CBT works, the role of accommodation behaviors in maintaining anxiety and teaching alternative strategies for accommodation, AF-CBT includes modules that focus on improving communication and behavioral interactions between the V/F dyad.

Persons delivering AF-CBT and iTCBT will include trained masters-level and doctoral-level clinicians working under the direct supervision of the PI. Co-I's [name] and [name] will lead all AF-CBT sessions. Participants will be closely monitored by Drs. [name] and [name], with their safety taking priority above the needs of the study. Our pilot work with Veterans at the MEDVAMC and community based outpatient clinics demonstrates the intensive weekend format to be a safe mode of treatment delivery. However, as an added level of precaution, the MEDVAMC has an emergency department with an on-call psychiatrist available 24 hours a day in the unlikely event that a patient needs immediate medical intervention.

Due to COVID-19 pandemic, participants will have the option to receive AF-CBT and iTCBT virtually via clinical video telehealth (CVT). At this time, the majority of outpatient mental health care at the MEDVAMC is being provided via CVT modalities and all clinicians are working remotely. Clinicians will provide treatments to participants in this study using approved platforms (e.g., VA Video Connect, BCM Zoom for Healthcare).

## **Section G: Sample Size/Data Analysis**

### **G1. Sample Size**

How many subjects (or specimens, or charts) will be used in this study?

Local: 94      Worldwide: 94

Please indicate why you chose the sample size proposed:

The sample size proposed in this study is appropriate for a feasibility trial. A total of 12 V/F dyads (24 participants) will be recruited for Phase 1 to refine the adapted AF-CBT intervention. In Phase 2 a total of 35 V/F dyads (70 participants) will be recruited to determine the feasibility/acceptability of, and satisfaction with, the intervention. This sample size was determined based on the number of referrals CITRAS received in the past year and the rate of monthly Veteran enrollment (9-11 per month) in our current trial. Because this study requires involvement of a family member, we conservatively estimated that about half of the Veterans enrolled each month would be eligible for this study. Although we do not expect a high rate of attrition, the sample of 35 accounts for 20% attrition. This ensures enough participants to provide robust feedback and will allow us to draw meaningful conclusions about the feasibility, acceptability, and satisfaction associated with this treatment.

## **G2. Data Analysis**

Provide a description of your plan for data analysis. State the types of comparisons you plan (e.g. comparison of means, comparison of proportions, regressions, analysis of variance). Which is the PRIMARY comparison/analysis? How will the analyses proposed relate to the primary purposes of your study?

Specific Aim 1 involves the adaptation and refinement of AF-CBT through an iterative process, guided by two adaptation frameworks. Qualitative interviews involves a data-coding process will use conventional and directed content analysis/coding techniques. The data coding process will be divided into three steps: (1) Open Coding, in which [name] and the PI independently review the recordings to identify key emerging themes; (2) Top-Level Coding will be applied to the remaining interviews and differences will be resolved through consensus. New themes that emerge will be added to existing codes. (3) Sub Coding will be applied to further refine broad constructs represented by top-level codes into sub-categories.

Specific Aim 2 will examine the feasibility/acceptability of, and satisfaction with, AF-CBT. Feasibility will be the percentage of V/F dyads who agree to participate out of the number invited to participate (benchmark of 50%). Retention rate will be the percentage of family members who attend both sessions of AF-CBT including the booster session (benchmark of 70%). Acceptability will be measured using the MTEI, in which a score > 27 indicates the treatment was found to be acceptable. Satisfaction will be assessed through the CSQ-8, where a score > 25 indicates satisfaction.

Specific Aim 3 will assess the internal validity and test-retest reliability of the FAS-A adapted for Veterans and their family members. Cronbach's alpha will be used to test the internal consistency of the measure and Pearson's r will be used to calculate test-retest correlation of the measure administered at different time points.

An exploratory aim will use Pearson's r to examine the association between changes on the Family Accommodation Scale-Anxiety with changes on the CRIS45 and BAI measures.

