### **J2. Consent Procedures**

Who will recruit subjects for this study?

PI

PI's staff

Describe how research population will be identified, recruitment procedures, any waiting period between informing the prospective participant and obtaining consent, steps taken to minimize the possibility of coercion or undue influence and consent procedures in detail.

The Center for Innovative Treatment of Anxiety and Stress (CITRAS) is a program in the Mental Health Care Line that provides specialty treatment of anxiety and stress-related disorders. Providers throughout the hospital including MEDVAMC community based outpatient clinics refer patients directly to CITRAS through an electronic consult for evaluation and specialty treatment. Veterans who are referred to CITRAS for treatment by their healthcare providers will be contacted by a CITRAS staff member and informed of treatment options including the opportunity to participate in this research study. If a patient expresses interest in participating in this study, we will discuss the protocol with them and schedule an appointment with them and their family members to meet with a member of the study team to discuss the study and conduct a baseline evaluation. If a patient is not interested in participating in this study but would nonetheless like treatment, they will be scheduled for treatment as routine clinical care.

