Any member of the study staff may obtain consent from study participants. This study will include Veterans and family members recruited from Houston and surrounding areas. Participants may also self-refer to the study through posted advertisements in Veteran newsletters or Veteran list-serves. People who self-refer to the study will be asked to confirm Veteran status and if they are enrolled as a patient at the MEDVAMC. If they are, a study appointment will be scheduled; if they are not currently enrolled at the hospital, they will be provided with the phone number for patient enrollment and invited to contact study personnel once they have completed this process. During the study appointment, a member of the study staff will describe the study and review all information in the informed consent form (see attachment in Section S), explaining the risks and benefits of participation. The consent form will be sent to participants via DocuSign, which has been approved for use in this study by VA ORD (see attachment in Section S). Standard operating procedures for how DocuSign will be used to obtain consent and where the electronic documents will be stored is outlined in the attachment in Section S.

Are foreign language consent forms required for this protocol?

No

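### Does the 50% feasibility benchmark leave out early refusals because dyads are counted as invited only at the joint appointment?

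*Combined protocol and SAP*

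**What the plan says.** Section G2, Specific Aim 2, defines the measure: "Feasibility will be the percentage of V/F dyads who agree to participate out of the number invited to participate (benchmark of 50"%). It does not say when a dyad becomes invited, what counts as agreeing, or which phase the rate covers. On phase, Section G1 helps: it assigns the question of feasibility to the 35 dyads of Phase 2.

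The recruitment steps are spread over three sections.

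- **J2, first contact.** Clinic staff contact referred Veterans and tell them about their treatment choices, this study among them. For a Veteran who is interested, the team will "schedule an appointment with them and their family members to meet with a member of the study team to discuss the study". Where a Veteran "is not interested in participating in this study but would nonetheless like treatment, they will be scheduled for treatment as routine clinical care".
- **F2, pre-screen.** Interested Veterans complete the Q-LES-Q-SF and the BAI. If both show enough impairment, "an appointment will be scheduled for interested Veterans and identified family members to complete a brief joint assessment".
- **J2, consent.** "During the study appointment, a member of the study staff will describe the study and review all information in the informed consent form". Section Q lists separate consent forms for Veterans and family members.
- **F1, inclusion criteria.** The Veteran must be someone who "has a family member willing to participate in the study".

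G1 gives the only planning figure that bears on relatives: "Because this study requires involvement of a family member, we conservatively estimated that about half of the Veterans enrolled each month would be eligible".

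**The concern.** The rate is per dyad, and the joint appointment is the first occasion on which staff are described as meeting both members. By then the Veteran has shown interest and passed the pre-screen, and a relative has been named. A Veteran who says no at first contact has gone to routine care. A relative who says no to the Veteran at home may never be seen by staff. If the team took the appointment as the invitation, the rate would be the share consenting among dyads already well disposed to the study.

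This would matter because G1 itself treats the need for a relative as the main limit on recruitment, and Section I says the pilot will inform a larger trial. An inflated uptake figure could lead that trial to expect recruitment it cannot achieve.

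**Working it through.** **1. The plan's own figures.** 12 + 35 = 47 dyads and 2 × 47 = 94 participants, as G1 states. The 35 is said to allow for 20% attrition: 35 × 0.80 = 28 completers, and 28/(1 − 0.20) = 35. (The 28 is derived, not stated.) No calculation lies behind the 50% benchmark. At exactly 50%, 35 consenting dyads correspond to 35/0.5 = 70 invitations, and 47 to 47/0.5 = 94.

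**2. How far the counting step can move the rate.** Let *a* be the share of dyads at the joint appointment who consent, and *d* the share of relatives asked who decline before it. Neither is in the documents, so both are assumed.

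- Counted at the appointment: rate = *a*.
- With earlier refusals by relatives counted: rate = *a*(1 − *d*).
- When *a* is at least 50%, the second rate falls below 50% only if *d* > 1 − 0.5/*a*.

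| Assumed *a* | *d* above which the result changes |
|---|---|
| 60% | 1 − 0.5/0.6 = 17% |
| 70% | 1 − 0.5/0.7 = 29% |
| 80% | 1 − 0.5/0.8 = 38% |
| 90% | 1 − 0.5/0.9 = 44% |

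With 35 consenting dyads and *a* = 70%, 35/0.7 = 50 dyads reach the appointment, a rate of 70%. If *d* = 20%, 50/0.8 = 62.5 relatives were asked and the rate is 35/62.5 = 56%, still above the benchmark. If *d* = 40%, 50/0.6 = 83.3 were asked and the rate is 35/83.3 = 42%, below it.

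**3. The same question per Veteran.** Let *w* be the share of Veterans offered the study whose dyad reaches the appointment. Uptake is *a* × *w*. At *a* = 70% it reaches 50% once *w* is at least 0.5/0.7 = 0.71. At *a* = 90% and *w* = 50%, 47 dyads need 47/0.9 = 52.2, so 53 dyads at the appointment (47/53 = 89%), and 47/0.45 = 104.4, so 105 Veterans (47/105 = 45%). The choice of denominator can therefore move the result across 50%.

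**4. What the documents support for these inputs.** They give no value for *a*, *d* or *w*. The one-half in G1 is an estimate of eligibility among Veterans enrolled in the team's current trial. It is not a refusal rate, and it also covers Veterans with no adult relative who meets the living or contact requirement in the inclusion criteria. Using it as *w* is a borrowing.

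**5. Whether the plan places the invitation at the appointment.** Set side by side, F2 calls that visit a joint assessment, and J2 describes it as a discussion of the study and a review of consent. Neither calls it the invitation. The earliest offer to referred Veterans is the first clinic contact in J2. Relatives are reached through the Veteran, so a Veteran offered dyadic participation can fairly be read as a dyad invited. On that reading a Veteran who is not interested, or whose relative says no, is in the denominator and not in the numerator.

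**6. Whether the appointment removes relatives' refusals.** It does not remove all of them. The pre-screen consists of two questionnaires completed by the Veteran and does not test the relative's willingness. A relative who has been named has not yet consented, has a separate consent form, and can decline at the visit. That refusal is counted under either reading.

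**The case for a change.** The best case for a change is that the first-contact reading has difficulties of its own. That contact is with a Veteran alone, it comes before the pre-screen, and it does not cover Veterans who refer themselves after seeing an advertisement. No recruitment log is described, and no section has staff asking the relative before the appointment. The other Aim 2 measures (retention, MTEI, CSQ-8) concern people already enrolled, so this rate is the only planned measure of whether dyads will join. Counts not kept during recruitment are hard to rebuild later.

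Some of this stands. The terms are undefined, and a refusal given at home could go unrecorded. But the difficulties are ordinary ones. Self-referred Veterans can be counted from their first conversation with the study team (F2), and those who fail the pre-screen can be shown as a separate loss. Counting from first contact takes in at least as many refusals as counting from the appointment, so it does not flatter the study.

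The obvious repair also gains little. A denominator that starts once the Veteran has passed the pre-screen and named a relative would still leave Veterans' own refusals out of the benchmark. If the team already counts from first contact, it could even raise the rate. Having staff approach relatives directly would add a recruitment step that J2 does not describe.

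**Conclusion.** The concern does not require a change. G2 leaves the counting step open, and the arithmetic shows that this can matter: 70% against 42% in one assumed example, 70% against 56% in another. But the claim that the benchmark misses early refusals depends on placing the invitation at the joint appointment, which the plan does not do. A reading that keeps those refusals in is at least as natural for referred Veterans. It is also too strong to say that relatives' willingness goes untested, since they can decline at consent.

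The size of any distortion is unknown, because every input to the calculation is assumed. The consequence is limited too. This is a single-arm pilot, the 50% is a descriptive mark with no test or go/no-go rule attached, and even a settled count of 35 out of 70 would carry an exact 95% interval of about 38% to 62%. What remains is missing detail. A team that counts from the first offer and reports its recruitment flow in the usual way, saying which step the rate starts from, would give a sound figure under the plan as written.
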